2.2 Protocol deviations

Important protocol deviations (or events) include changes to the procedures that may impact the quality of data. The following will be considered an important protocol deviation. These deviations will be listed and discussed in the CSR as appropriate:

- Patients entered but who did not receive study treatment (Deviation 1).

Deviation 1 will lead to exclusion from the safety, PK and PET analysis set. Patients who receive the wrong treatment at any time (provided they receive at least 1 administration of [¹¹C]osimertinib and/or oral osimertinib) will still be included in the safety analysis set as

described in section 2.

During the study, decisions on how to handle errors in treatment dispensing (with regard to continuation/discontinuation of study treatment or, if applicable, analytically) and any other important protocol deviation will be made on an individual basis with written instruction from the study team leader, appropriate study personnel and/or statistician.

The important protocol deviations will be listed and summarised across all patients.

3. PRIMARY AND SECONDARY VARIABLES

3.1 Parameters of brain exposure of [¹¹C]osimertinib

The primary outcome variables describe the distribution of [¹¹C]osimertinib in the whole brain using a set of exposure parameters including:

- $C_{max, \%ID\ brain}$ Maximum radioactivity concentration in brain (%), expressed as the percentage of injected radioactivity (calculated as the radioactivity concentration in the region of interest multiplied with the volume of the region of interest), divided by the radioactivity injected, and multiplied by 100
- $C_{max,SUV\ brain}$ Maximum radioactivity concentration in brain, expressed as the standardized uptake value corresponding to the regional radioactivity concentration normalized for injected radioactivity and body weight
- $T_{max\ brain}$ Time of maximum radioactivity concentration in the brain (min), obtained directly from the observed concentration versus time data
- $AUC_{brain\ 0-90}$ Area under the brain radioactivity concentration-time curve between 0 and 90 minutes (SUV*min) after injection calculated by the linear trapezoidal rule
- $AUC_{blood\ 0-90}$ Area under the plasma radioactivity concentration-time curve between 0 and 90 minutes (SUV*min) after injection calculated by the linear trapezoidal rule
- K_p Brain plasma partition coefficient – ratio of radiolabelled drug in brain to that in plasma calculated as $AUC_{brain\ 0-90}/AUC_{blood\ 0-90}$
- V_T Total distribution volume (ml/cc) quantified using kinetic compartment model

Radioactivity concentrations (as %ID) for the whole brain, tumour regions and anatomical regions will be plotted as time activity curves for individual subjects as well as an overlain plot for all subjects with arithmetic mean curve. These figures along with PET images after administration of [¹¹C]osimertinib will be prepared by the AZ PET Centre at Karolinska Institutet.

Exposure parameters will be summarised for all subjects in the PET analysis set using descriptive statistics. Geometric mean and geometric CV% will not be calculated for T_{max} brain. A by-subject appendix of individual exposure parameters will be provided.

Note: Some PET data variables may need to be amended after evaluation of first few patients, depending on the emerging data and selection of analysis method (kinetic modelling approach). Additionally, the PET team at KI may calculate exposure and/or efficacy parameters, other than those listed above. Subsequently, additional listings, summary tables, and figures may be added to the planned presentation of data. These modifications will be covered in a future SAP amendment when data from first few subjects are available.

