1.2 Rationale for study design, doses and control groups

Osimertinib has been shown to be active in treating patients with EGFRm+ NSCLC having pre-existing BM and/or has potential to slow down or prevent development of new BM. Preclinical studies in mice, rats and monkeys show that osimertinib crosses the intact BBB of animals and has good exposure in the brain regions of interest (ROIs). It is hypothesized that the efficacy of osimertinib in the BM is because of its high BBB penetration in both normal and metastatic regions in the brain.

The study will determine the distribution of [¹¹C]osimertinib in the brain of patients with EGFRm+ NSCLC with BM. It is hypothesized that the brain distribution of osimertinib is at least similar compared to the distribution in healthy subjects with an intact BBB (see Section 1.1.3) and it is at least similar at steady state compared to that observed after a single dose. This evaluation of osimertinib BBB penetration in patients with NSCLC will support further use of osimertinib in other CNS mediated oncology indications. The study design includes 2 phases for patients, the first (imaging) phase consisting of single IV microdose administrations of [¹¹C]osimertinib and PET examinations on 3 occasions (baseline, post single dose and post repeat dose) and the second phase consists of continued oral administrations of osimertinib.

The study will test the following hypotheses:

1. Osimertinib penetrates the BBB in patients with NSCLC and BM (including leptomeningeal metastases [LM]); whole brain exposure >1% injected dose.
2. Whole brain and BM exposure of osimertinib at steady state is similar or higher compared to single dose.
3. There may be changes in the size and number of BM at 3 weeks of treatment with osimertinib.
4. Changes in the size and number of BM at 3 weeks correlate to the regional [¹¹C]osimertinib exposure.
5. Higher [¹¹C]osimertinib levels in BM or LM reflect higher [¹¹C]osimertinib exposure and/or binding to EGFR.

6. Exposure of osimertinib to BM region will be at least similar to that of the non-metastatic brain regions.

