1.4 Study design

This is an open-label, single centre Phase I study to determine the brain exposure of [¹¹C]osimertinib in patients with NSCLC. This study will be conducted in patients with EGFRm NSCLC with BM. The study will consist of 2 phases, an imaging phase and a CAP (Figure 1A). The patient's participation in the imaging phase of the study will be approximately 32 days. The imaging phase of the study will include 3 single intravenous microdose administrations of [¹¹C]osimertinib and positron emission tomography examinations on: Day 1, Day 2 (or up to Day 8) and Day 29 (see Section 5.3.2). Osimertinib 80 mg once a day will be taken by the patient from the day of the second PET examination for at least 21 days before the PET3 examination will be scheduled.

Positron emission tomography examinations using a microdosing approach (Lee and Farde 2006, Saleem et al 2015) will be used, i.e. osimertinib will be labelled with ¹¹C and administered IV at a microdose (<10 µg).

A sufficient number of eligible patients (approximately 12) will be enrolled in order to obtain at least 8 evaluable patients with BM. An evaluable patient is defined as a patient who completes at least 2 PET examinations; 1 with a single IV microdose of [¹¹C]osimertinib alone and another with a co-administered oral 80 mg osimertinib and [¹¹C]osimertinib microdose administration.

The identified study population is considered sufficient to examine variability in pharmacokinetic (PK) and PET examinations. The patients will need to have confirmed EGFRm status by either local or central testing. Epidermal growth factor receptor mutation positive status can be confirmed via assessment of tissue or cytological sample from primary or metastatic tumour. All patients will have a baseline brain MRI for eligibility (presence of BM) and for anatomical and manual delineation of brain regions to be applied in PET image analysis (and for detection of BBB disruption). **CCI**

Brain MRI will include (but is not limited to) T1 (gadolinium enhanced), T2/FLAIR and diffusion-weighted imaging (DWI).

Thorax/abdomen CT will be performed as routine clinical examination and will serve for the diagnosis and evaluation of primary lung tumour and other metastatic sites. It will be repeated at the end of study treatment (on Day 25 ±4 days), to follow potential early effects on tumours.

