8.3 Definitions of analysis sets

8.3.1 PET analysis set

All patients who complete at least 2 PET examinations will be included in PET data analysis and evaluation of [^{11}C]osimertinib brain distribution. Patients who have completed all PET examinations; will be included in the assessment of potential treatment effects.

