2. ANALYSIS SETS

2.1 Definition of analysis sets

There will be 4 analysis sets considered in this study:

- The *safety analysis set* will include all patients who receive at least 1 administration of [¹¹C]osimertinib and/or osimertinib
- The *PET analysis set* will include all patients who complete at least 1 PET examination for the evaluation of [¹¹C]osimertinib brain distribution.
- The *complete PET analysis set* will include all patients who complete all three PET examinations. This analysis set is a subset of the PET analysis set and will be used in the assessment of potential treatment effects on brain metastases
- The *PK analysis set* will include all patients who received at least 1 administration of either [¹¹C]osimertinib and/or osimertinib and had post administration PK assessments of osimertinib and/or its metabolite (AZ5104) without any CSP deviations or dosing deviations that might have affected the PK analysis.

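### Hypotheses 2 and 6 are within-patient comparisons, but the visible SAP plans no PET3/PET2 or metastasis/non-metastatic ratio and plots regional curves on a scale that depends on region volume

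*SAP*

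**What the plan says.** Protocol 1.2 introduces six hypotheses with "The study will test the following hypotheses". The second is "Whole brain and BM exposure of osimertinib at steady state is similar or higher compared to single dose". The sixth is "Exposure of osimertinib to BM region will be at least similar to that of the non-metastatic brain regions". Protocol 7.2 plans three tracer administrations for every patient, and SAP 1.1 applies all exposure parameters to tumour, whole brain and anatomical regions. Both comparisons can therefore be made within a patient.

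For the analysis, SAP 3.1 states that "Exposure parameters will be summarised for all subjects in the PET analysis set using descriptive statistics", with individual values in a by-subject appendix. SAP 4.1 lists the usual descriptive statistics and adds the geometric mean and coefficient of variation for exposure parameters. Protocol 8.5 and 8.5.7 add no contrast between scans or regions. The only PET ratio defined is Kp, brain to plasma.

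On patients, the SAP 2.1 PET analysis set needs at least one examination. Protocol 8.3.1 has "All patients who complete at least 2 PET examinations will be included in PET data analysis". SAP 2.1 also defines a complete PET set of patients with all three scans, which "will be used in the assessment of potential treatment effects on brain metastases". Protocol 8.3.1 gives patients with all scans to the assessment of potential treatment effects, without restricting that to metastases.

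On scale, SAP 3.1 plots time-activity curves for whole brain, tumour and anatomical regions as %ID. It defines %ID as regional concentration times regional volume, as a percentage of the activity injected. It also defines Cmax on the SUV scale, AUCs in SUV*min, Kp and VT.

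**The concern.** A paired question is given an unpaired description. If the PET2 and PET3 summaries rest on different patients, the contrast between them mixes any change in exposure with a change of patients.

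The documents foresee such patients. Protocol 1.4 says "An evaluable patient is defined as a patient who completes at least 2 PET examinations": one with the microdose alone and one with oral dosing, which PET1 plus PET2 satisfies. Oral dosing runs "from the day of the second PET examination for at least 21 days before the PET3 examination", and Protocol 6.8 takes a patient who needs a dose reduction out of the imaging phase. Losses between PET2 and PET3 may therefore be related to tolerability and need not be random.

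The report could then describe exposures as similar with no estimate of within-patient change and no statement of its uncertainty. If the ratios are worked out later from the appendix, someone must choose the parameter, how to combine several lesions in a patient, and whom to include, all after seeing open-label data.

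The %ID curves are a separate difficulty. A small lesion and a large region at the same concentration plot at very different heights, so the one regional figure planned cannot show hypothesis 6.

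**Working it through.** The documents give no patient variability, margin, alpha or power for these comparisons, so there is no figure of the plan's own to reproduce. Protocol 8.2 sets at least 8 completers from about 12 patients by convention. All figures below are illustrations.

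**1. Precision of a paired ratio.** Inputs: n = 8 (Protocol 8.2); within-patient CV assumed at 10%, 20% or 40%; true ratio 1.00.

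- Log-scale SD: σw = sqrt(ln(1 + CV²)) = 0.0998, 0.198, 0.385.
- 95% limits: exp(± t(0.975, 7) × sqrt(2) × σw / sqrt(8)). With t = 2.365 and sqrt(2)/sqrt(8) = 0.5, the exponent is 1.182 × σw.
- Results: 0.89-1.13, 0.79-1.26, 0.63-1.58.

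**2. What pairing gains.** As a yardstick only, suppose someone formed an unpaired interval from 12 patients at PET2 and 8 at PET3. The SAP plans no such interval. The only variability figure in the documents is 1.29 ± 0.42 %ID in three primates (Protocol 1.1.3). If ± is an SD, the CV is 0.42/1.29 = 32.6%, with its own 95% interval of about 17% to 205%. Borrowing 32.6% as the between-patient CV gives σb = 0.317.

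- Limits: exp(± t(0.975, 18) × sqrt(σb² + σw²) × sqrt(1/12 + 1/8)), with t = 2.101.
- At within-patient CV 10%, 20%, 40%: 0.73-1.38, 0.70-1.43, 0.62-1.61.
- At between-patient CV 20% and within-patient CV 40%: 0.66-1.52, slightly narrower than the paired 0.63-1.58.

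Pairing helps clearly if within-patient variability is low, and little or not at all at 40%.

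**3. Change of patients alone.** If k of 12 patients are lost at random after PET2, the ratio of geometric means moves within exp(± 1.96 × σb × sqrt(1/(12 − k) − 1/12)) with no true change. At σb = 0.317:

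- k = 1: 0.95-1.06
- k = 2: 0.92-1.08
- k = 4: 0.88-1.14

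The documents do not say when losses are expected, so 4 is the upper case if 8 complete. With one or two random losses this is smaller than the paired uncertainty at CV 20%. Non-random loss is not captured.

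**4. The %ID scale.** Whole brain is taken at about 2 %ID (healthy volunteers, Protocol 1.1.3). Brain volume of 1,300 mL and spherical lesions are assumptions. Lesion volume is π/6 × d³.

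- 10 mm: 0.524 mL; 2 × 0.524/1,300 = 0.0008 %ID.
- 20 mm: 4.19 mL; 2 × 4.19/1,300 = 0.0064 %ID.

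Both are at the same concentration as the whole brain; the gap is volume only. If a lesion region were redrawn after its diameter fell by 10%, 20% or 30%, its %ID would fall to 0.9³ = 73%, 0.8³ = 51% or 0.7³ = 34% with concentration unchanged.

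**The case against.** The plan calls itself descriptive (Protocol 8.2, SAP 1.3), and these hypotheses sit in the design rationale, not among the objectives. That stands: no test is missing and none is asked for. A within-patient ratio is itself a descriptive summary. Since the protocol gives no margin for similarity, an interval would show uncertainty but would not settle either hypothesis.

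The data are not lost. The appendix holds every individual value, each summary reports n, and Cmax on the SUV scale, SUV-based AUC, Kp and VT are planned by region. A reader might infer that hypotheses 2 and 6 cannot be answered, or that every regional result is distorted by volume. Neither follows. The volume problem is confined to the %ID curves and regional Cmax in %ID; what is missing is a prespecified contrast.

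Protocol 8.3.1 can be read as already reserving patients with all three scans for comparisons over treatment. That also stands, and makes the remedy partly one of aligning SAP 2.1. Patient loss bears only on hypothesis 2, because hypothesis 6 is a same-scan comparison.

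A reader might also infer that the lesion region at PET3 is undefined. Protocol 1.4 refers to delineation on the baseline MRI, and Protocol 5.1 to delineation on the scans for the corresponding PET analysis. Text is blacked out next to the first of these and in the brain MRI footnote to Table 1, so a rule may exist there.

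Finally, SAP 3.1 foresees an amendment that may add tables and figures. It names neither comparison, and it awaits data from the first patients.

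**Conclusion.** The point holds as a low-cost improvement that should be made. The visible SAP describes each exposure parameter separately, in a set where PET2 and PET3 can rest on different patients, while the protocol poses two within-patient comparisons. The ratios are recoverable, but they are not prespecified and carry no interval.

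The %ID curves cannot show hypothesis 6. They would mislead on hypothesis 2 in metastases only if the region is redrawn as lesions shrink, which the visible text does not settle.

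The size is uncertain. The paired limits in 8 patients rest on assumed within-patient CVs, and no patient CV is in the documents. The gain from pairing runs from clear at 10% to little or none at 40%. The case for the change therefore rests mainly on matching the summary to the question and fixing the choices in advance, not on a promised gain in precision. Blacked-out exploratory text could not be checked.

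**What to change.** Put the following into the SAP amendment foreseen in SAP 3.1, as estimation with no tests, and fix the choices without reference to the early patients' results.

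- **Hypothesis 2.** In patients with both scans, report the within-patient PET3/PET2 geometric mean ratio with 95% CI and the individual ratios, for Cmax on the SUV scale in whole brain and in metastases. This needs no blood input. Add AUC0-90, Kp and VT where scan duration and type of blood input match, stating n, because Protocol 1.4 accepts 60-minute scans and Protocol 5.3.2.2 allows arterial sampling to be dropped at PET3. Extending the use of the complete PET set in SAP 2.1 would do this and agree with Protocol 8.3.1.
- **Hypothesis 6.** Report the same-scan ratio of metastasis to non-metastatic brain with 95% CI on SUV, and on Kp or VT where available, with one prespecified rule for combining lesions within a patient.
- **Figures.** Plot regional time-activity curves in SUV as well as %ID.
- **Regions.** Confirm that the same delineation rule applies at PET2 and PET3, unless blacked-out text already says so.

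The cost is a few table and figure shells, with no new data or patients. Intervals will be wide at n = 8, and some AUC0-90, Kp and VT ratios may be missing.

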3.2 PK Variables

All PK concentrations will be listed. Average of the concentrations between the PET measurement will also be summarised. Summary data for patients in the PK analysis set will be presented in the table. The following PK parameters will be summarized for patients in the PK analysis set. There will be no PK parameters presented for patients after the first dose (PET2 day) and only steady state PK parameters (PET3) will be calculated.

Pharmacokinetic parameters for an individual patient were not included in the summaries if the patient missed a single dose within 3 days of the planned PK sampling, received a different dose on the PK sampling day or ≥ 7 days of dosing were missed with <10 days back on daily administration before the PK sampling day. This list of patients was provided by the pharmacokineticist. The pre-dose time point on PET3 was also used as the 24 hr time point to calculate the AUC_{ss} since at the time of PET3, if the patient met the above criteria, osimertinib and AZ5104 are expected to be at steady state.

Osimertinib: Area under the concentration time curve from 0-24 hrs at steady state (AUC_{ss}), maximum plasma concentration at steady state (C_{ssmax}), time of maximum plasma concentration at steady state (T_{ssmax}), apparent clearance at steady state (CL_{ss}/F).

AZ5104: AUC_{ss}, C_{ssmax}, T_{ssmax}, AZ5104 AUC_{ss}/osimertinib AUC_{ss}, AZ5104 C_{ssmax}/osimertinib C_{ssmax}.

For PET2, ie, after single dose of osimertinib, no PK parameters will be presented due to planned limited sampling and only the concentration data will be listed and summarized.

Events or changes to procedures that may impact the evaluation of PK data including, but not limited to, vomiting following oral dosing occurring within the timeframe of 2 times the median t_{max}, wrong dose administered, patient received a prohibited concomitant medication,

sample processing errors that lead to inaccurate bioanalytical results, and incomplete PK profile. The final decision on the inclusion of the patient in the PK analysis set will be determined by the PK scientist and documented in the CSR. The affected PK data collected (as deemed by the study pharmacokineticist) will be excluded from the summaries and statistical analyses, but will still be reported in the study result listings. Pharmacokinetic parameters for an individual patient may not be included in the summaries if the patient missed a single dose within 3 days of the planned PK sampling, received a different dose on the PK sampling day or ≥ 7 days of dosing were missed with <10 days back on daily administration before the PK sampling day. This list of patients will be provided by the pharmacokineticist. The pre-dose time point on PET3 may also be used as the 24 hour time point to calculate the AUC_{ss} as at the time of PET3, if the patient met the above criteria, and osimertinib and AZ5104 are expected to be at steady state.

CSF analysis:

The CSF concentration will be listed for all patients and summarized for patients in the PK analysis set. The CSF to plasma and CSF to free plasma ratio will be listed for all patients and summarized for patients in the PK analysis set. The free fraction value to 5.27% free for osimertinib and 7.92% for AZ5104 will be used for the free plasma calculation based on the in vitro plasma protein binding assessments.

3.3 Safety and tolerability variables

Safety and tolerability will be assessed by:

- Assessment of adverse events (AEs), graded by Common Terminology Criteria for Adverse Events (CTCAE) (v4.03)
- Physical examination
- Vital signs (including blood pressure [BP], pulse rate, body temperature, and weight)
- Standard 12 lead electrocardiograms (ECGs)
- Evaluation of laboratory parameters (clinical chemistry, coagulation, haematology and urine analysis)
- Echocardiogram/multiple gated acquisition scan (MUGA)
- Concomitant medications

Adverse events will be classified according to the terminology of Medical Dictionary for Regulatory Activities (MedDRA), Version 21.0 or higher (preferred term and system organ class [SOC]).

Adverse events reported before any administration of osimertinib will be listed only and be referred to as “pre-treatment”. Similarly, AEs reported before any administration of osimertinib that continue after the first administration without worsening will also be classified as “pre-treatment”.

A treatment emergent AE (TEAE) will be defined as any AE with start date and time on or after the first IV dosing of osimertinib in imaging phase up to 30 days after their last study treatment administration or immediately before initiation of any other cancer therapy, whichever occurs first.

For laboratory data, vital signs and ECG data, baseline is defined as the latest result obtained prior to the first IV dose of osimertinib in the imaging phase.

For all safety data, an on-treatment period is from after the first IV dose of osimertinib in the imaging phase, up to and including the follow-up visit.

Patients not participating in the continued access phase or who discontinue treatment during the imaging phase will return to the clinic for follow-up assessments 30 days (± 7 days) after their last administration of osimertinib in the imaging phase. If the patient’s last administration of osimertinib is in the continued access phase, the patient will be contacted 30 days after their last administration of osimertinib to follow up on any existing AEs/SAEs and monitor for new AEs/SAEs that may be related to the IP, and record any sudden deaths of unknown cause. This follow-up assessment will serve as the end-of study assessment for a patient.

Concomitant medications are those which were taken at any time between first dose of osimertinib in the imaging phase and completion of or withdrawal from the study. This includes medications which were started before first IV dose of osimertinib in the imaging phase, but stopped during the course of study (after first IV dosing date/time) or were ongoing at completion of or withdrawal from the study.

Exposure to [^{11}C]osimertinib will be summarized by number of patients receiving 1, 2 or all 3 doses.

Exposure to oral osimertinib, during imaging phase, will be assessed using total exposure time and actual exposure time

- Total exposure time (months) will be calculated from the first dose to the last dose

$$\begin{aligned} & \text{Total exposure} \\ & = \frac{(\text{last dose date where dose} > 0 \text{ mg} - \text{first dose date}) + 1}{30.4375} \end{aligned}$$

- Actual exposure time (months) will be calculated from first dose to the last dose, taking account of dose interruptions.

Actual exposure

$$= \frac{[(\text{last dose date where dose} > 0 \text{ mg} - \text{first dose date}) + 1 - \text{total duration of dose interruption (i. e. number of days with dose} = 0\text{mg})]}{30.4375}$$

